Title of the study:

Impact of renal replacement therapy modality on coagulation and platelet function in critically ill patients: Intermittent hemodialysis vs. continuous renal replacement therapy

The National Clinical Trial (NCT) number: NCT04512131

Date of the documenta: December 20, 2023

Study Protocol wih Statistical Analysis Plan (SAP)

Study Protocol

Study design and patients

This was a single-center prospective observational study. The institutional review board at Seoul National University Hospital approved the protocol (H-2007-102-1141). Patients or their surrogates provided written informed consent before enrollment.

Adult patients admitted to a surgical or medical intensive care unit (ICU) and were underwent a session of iHD or at least 48 hours of CRRT or both modalities between August 2020 and January 2023 were included. Patients were excluded if they fulfilled one of the following criteria: duration of CRRT was less than 48 hours, received platelet concentrates, fresh frozen plasma, or cryoprecipitate, discontinuation or initiation of the antiplatelet agents or anticoagulants during the study period, technical errors in laboratory tests.

Renal replacement therapy

All patients underwent either iHD or CRRT or both, according to the clinical situation. The detailed setting of RRT including blood flow rate, dialysis flow rate, ultrafiltration rate, duration, and use of anticoagulants was determined by nephrologists and intensivists. Patients were divided into the iHD or CRRT group according to the applied RRT modality. If both methods were applied to a patient, data from both modalities were included in the analysis. Each patient was exposed to a single episode of iHD or at least 48 hours of continuous venovenous hemodiafiltration or both. In the iHD group, hemodialysis was applied for 2 to 4 hours depending on the clinical condition of patients. Since maintenance iHD is usually performed 3 times a week, 48 hours of CRRT was deemed comparable to a single session of iHD.

Laboratory investigations

In the iHD group, blood samples were obtained immediately before and after the hemodialysis session. In the CRRT group, blood samples were taken within 24 hours of initiation of CRRT and the second samples were taken 48 hours after collection of the first samples.

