The primary study outcome was changes in CT of EXTEM after dialysis. Secondary outcomes included changes in other EXTEM and FIBTEM parameters, AUC of platelet aggregometry, platelet count, PT, aPTT, fibrinogen concentration, D-dimer concentration, the activity level of protein C and protein S, bleeding events, and transfusion requirements after dialysis. Laboratory test results were compared before and after the application of each dialysis modality. To identify differences in changes according to dialysis modality, a comparison of each study outcome was made between the iHD group and the CRRT group. Bleeding events and transfusion requirements within 24 hours after dialysis in the iHD group or within 24 hours after the second blood sample collection in the CRRT group were also compared between the two groups. The severity of bleeding events were graded

by the modified World Health Organization bleeding scale.

SAP

Based on a previous study regarding the reproducibility of ROTEM results, the mean (\pm standard deviation) CT of EXTEM was set as 55 ± 6.9 seconds before dialysis. An absolute difference of 5 seconds in CT after dialysis was deemed significant. With a two-sided type-I error of 0.05 and a power of 80%, the required sample size was calculated to be 60 patients. Considering a loss to follow-up of 40%, the sample size was increased to 50 patients in each group, resulting in a total sample size of 100 patients.

Normally distributed continuous data were described as means and standard deviation and non-normal distributed data were described as a median and interquartile range [25th–75th interquartile range]. The normality of continuous data was assessed through the Shapiro-Wilk test. Comparisons between groups were performed by using the Student t-test or the Mann-Whitney U test for the continuous variables normally or non-normally distributed, respectively. Categorical variables were reported as numbers and percentages. Categorical data were compared with a chi-square test. A P value less than 0.05 was considered statistically significant and statistical analysis was performed using IBM SPSS 27.0 (IBM Corp, Armonk, NY, USA).

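### In patients who move from CRRT to iHD, the 24 h CRRT event window stays open after iHD starts, so a bleed or transfusion can count in both groups, or for CRRT while the patient is on iHD

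*Combined protocol and SAP*

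**What the plan says.** All of the following is in the combined protocol and SAP.

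- **Renal replacement therapy** puts a patient who had both treatments in both groups: "If both methods were applied to a patient, data from both modalities were included in the analysis". Exposure is described as "Each patient was exposed to a single episode of iHD or at least 48 hours of continuous venovenous hemodiafiltration or both", with no order and no minimum gap between modalities. For iHD, "hemodialysis was applied for 2 to 4 hours depending on the clinical condition of patients".
- **Laboratory investigations** fixes the CRRT sampling times: "blood samples were taken within 24 hours of initiation of CRRT", and "the second samples were taken 48 hours after collection of the first samples".
- **Study outcomes** sets one event window per modality: "Bleeding events and transfusion requirements within 24 hours after dialysis in the iHD group or within 24 hours after the second blood sample collection", the second being the window for CRRT. The groups are then compared on these events.
- **SAP** compares categorical data with a chi-square test, with no term for patients who appear in both groups.

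No section cuts the CRRT window at a change of modality, assigns an event to a single modality, or bars counting an event twice.

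**The concern.** The CRRT window runs from a blood draw whether or not CRRT is still running. Suppose the second CRRT sample is at hour 0 and iHD runs from hour 6 to hour 10. A bleed at hour 12 is within 24 h of the sample and within 24 h after dialysis, so it is an event in both groups. A bleed at hour 8 comes before the iHD window opens but inside the CRRT window, so it is a CRRT event although the patient is on iHD. Both results come from following the stated rules exactly.

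Bleeding and transfusion are the clinical outcomes of a study that is otherwise about laboratory values, and the plan compares them between modalities. An event shared by two groups, or booked to the modality no longer running, blurs that contrast in the patients who supply data to both sides. The chi-square test treats the groups as independent and cannot detect or correct this.

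**Working it through.** **The plan's own figure.** The only calculation in the SAP is the sample size for EXTEM CT (difference 5 s, SD 6.9 s, two-sided 0.05, power 80%). Per group: 2 × (1.960 + 0.842)² × 6.9² / 5² = 29.9, so 30 per group and 60 in total. With 40% loss, 60 / (1 − 0.40) = 100. Both figures reproduce, and neither depends on the present point. They do supply a denominator for scale: 50 × 0.60 = 30 evaluable per group.

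**Overlap of the windows.** Put the second CRRT sample at hour 0. Let iHD start at hour s, at or after that sample, and last d hours, where d is 2 to 4.

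- CRRT window: 0 to 24.
- iHD window: s + d to s + d + 24.
- Shared time: max(0, 24 − (s + d)).
- Session time that counts for CRRT only: from s to the earlier of s + d and 24.

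| iHD start s (h) | Shared time, d = 2 (h) | Shared time, d = 4 (h) | Session time inside CRRT window, d = 2 / d = 4 (h) |
|---|---|---|---|
| 6 | 16 | 14 | 2 / 4 |
| 12 | 10 | 8 | 2 / 4 |
| 18 | 4 | 2 | 2 / 4 |
| 20 | 2 | 0 | 2 / 4 |
| 22 | 0 | 0 | 2 / 2 |
| 24 | 0 | 0 | 0 / 0 |

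Double counting therefore needs s < 22 for a 2 h session or s < 20 for a 4 h session. Misattribution of events during the session is possible for any s < 24.

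**Reverse order.** The second CRRT sample falls 48 to 72 h after CRRT starts. If iHD comes first, its window closes 24 h after the session ends, and the CRRT window opens at least 48 h after CRRT starts. The gap is at least 48 − 24 = 24 h, so the windows cannot overlap.

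**Size, under assumptions.** The documents give no switcher count, switch times or event rates. Assume a constant hazard, d = 4, and a 24 h event risk p. The chance of an event in h shared hours is 1 − (1 − p)^(h/24).

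| 24 h risk p | s = 6 (h = 14) | s = 12 (h = 8) |
|---|---|---|
| 5% | 2.9% | 1.7% |
| 10% | 6.0% | 3.5% |
| 20% | 12.2% | 7.2% |

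- Low end: 5 switchers × 1.7% = 0.085 events; 0.085 / 30 = 0.3 percentage points.
- High end: 10 switchers × 12.2% = 1.22 events; 1.22 / 30 = 4.1 points.

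With no switchers in the relevant interval, the effect is zero.

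**The case against.** The case for leaving the plan alone has several parts.

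- **The size may be negligible.** This stands. Five to ten switchers would be 17 to 33% of a group of 30, all switching within one particular day, and nothing in the documents supports that number.
- **The exclusions remove some cases.** This stands in part. Recipients of platelet concentrates, plasma or cryoprecipitate are excluded, as are patients whose antithrombotic drugs were started or stopped. The study period that limits these exclusions is not defined, so they may not reach the whole event window. They also leave bleeding events and red-cell transfusion untouched.
- **A fixed 24 h lag after each exposure is defensible.** As a way of capturing delayed effects it is. A bleed minutes into iHD after two or three days of CRRT is not obviously an iHD event. But this does not justify counting one event in both groups of a comparison that treats them as independent.
- **The outcomes are secondary.** This stands.

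A reader might also infer more than the documents support:

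- **That every switch within a day double counts.** It does not; the limit is 20 to 22 h, and an event must fall in the shared time.
- **That the distortion reaches 3 to 10 points.** That needs a 20 to 30% risk inside the overlap. With 14 shared hours it implies a 24 h risk of 1 − 0.8^(24/14) = 32% to 1 − 0.7^(24/14) = 46%, which no figure in the plan supports.
- **That the net bias has a known direction.** An event added to two equal groups leaves the risk difference unchanged and pulls the ratio toward 1, while events during iHD raise the CRRT count. How these combine depends on true rates that are not given.

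**Conclusion.** The point holds for patients who step down from CRRT to iHD. The stated windows count an event in both groups when it falls in the shared time, which exists if iHD starts less than 20 h (4 h session) to 22 h (2 h session) after the second CRRT sample. They credit an event during iHD to CRRT alone for any start before 24 h. Patients who go from iHD to CRRT have no overlapping event windows.

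The consequence is confined to bleeding and transfusion, in practice mainly red-cell transfusion. The size cannot be determined from the documents. The illustrative range of 0.1 to 1.2 double-counted events (0.3 to 4 points on 30 per group) rests on the assumed switcher numbers, event risks and timing, and zero is also possible. It does not include events during the session that are credited to CRRT. The primary outcome and sample size are unaffected. The change is worth making because it is cheap, and because one event can matter in a comparison of about 30 per group.

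**What to change.** 1. Count each event once. End the CRRT event window at the earlier of 24 h after the second sample or the start of iHD.
2. Open the iHD event window at the start of the session for all iHD patients. Without this step, closing the CRRT window would leave an event during the session in neither window. Making the change only for switchers would count such events differently from those of iHD-only patients.
3. Report how many events fell in overlapping windows.
4. Repeat the bleeding and transfusion comparison without patients whose iHD began within 24 h after the second CRRT sample. If event onset times were not recorded, use this sensitivity analysis alone.

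**Cost.** New wording for the outcome definition and re-coding of timed events; no new patients or samples. The plan does not say that onset times were recorded, so this must be checked first. Some CRRT windows become shorter than 24 h, and the cut-off is a clinically decided switch, which may be informative, so the number and length of shortened windows should be reported. If the iHD window still closes 24 h after dialysis, it lengthens by the 2 to 4 h session, to 26 to 28 h, and this should be stated. Changing to rates per patient-hour is not required.

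### The 80% power figure uses the SD of a single pre-dialysis CT, is not tied to a contrast, and is not established for the iHD vs CRRT difference in change; the named tests assume independent groups and unpaired data

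*Combined protocol and SAP*

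**What the plan says.** Under Study outcomes, "The primary study outcome was changes in CT of EXTEM after dialysis". Two analyses follow. One is within modality: "Laboratory test results were compared before and after the application of each dialysis modality". The other is between modalities: "To identify differences in changes according to dialysis modality, a comparison of each study outcome was made between the iHD group" and the CRRT group. Neither is labelled as the main one.

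The SAP's inputs are a pre-dialysis value ("CT of EXTEM was set as 55 ± 6.9 seconds before dialysis"), taken from a reproducibility study, and an effect: "An absolute difference of 5 seconds in CT after dialysis was deemed significant". It continues: "With a two-sided type-I error of 0.05 and a power of 80%, the required sample size was calculated to be 60 patients". Attrition is then added: "Considering a loss to follow-up of 40%, the sample size was increased to 50 patients in each group", for a total of 100. No formula, SD of change or pre/post correlation is given.

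For continuous data the SAP names only this: "Comparisons between groups were performed by using the Student t-test or the Mann-Whitney U test for the continuous variables", chosen by normality. The Renal replacement therapy section says that a patient treated with both modalities contributes data under each.

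**The concern.** The spread of a change is not the spread of a single measurement. If CT before and after dialysis correlate weakly, the change is more variable than one CT; if strongly, less. Using 6.9 s directly as the SD of change assumes rho = 0.5 without saying so. A reader who meets a null iHD vs CRRT result will weigh it against the stated 80%, so it matters whether that figure applies to this contrast.

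The second problem concerns validity. Student t and Mann-Whitney tests treat the two groups as separate people. If some patients are in both, the standard error is wrong, in a direction set by the correlation of a patient's two changes. The same tests do not suit a before/after comparison, where each patient supplies both values.

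**Working it through.** **Inputs from the SAP:** two-sided alpha 0.05, power 80%, SD 6.9 s at one time point, difference 5 s, loss 40%, 50 per group. **Assumed, because the documents do not give them:** rho (0 to 0.7), equal SDs before and after, the same SD and rho in both modalities, number of shared patients, and correlation c of their two changes.

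**1. Reproducing the 60.**
- Two independent groups: 2 × (1.960 + 0.842)² × (6.9/5)² = 29.9, so 30 per group and 60 in total.
- Paired, within one modality, rho = 0: (1.960 + 0.842)² × (2 × 6.9²)/5² = 29.9, so 30 per modality and again 60.
- Attrition: 60/(1 − 0.40) = 100.

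The arithmetic is right, but the result cannot tell the two readings apart. Nor can the per-group target, since 30 per modality follows from either.

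**2. Power for a 5 s effect on the scale of change.** SD of change = 6.9 × √(2(1 − rho)); power from the noncentral t distribution.

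| Assumed rho | SD of change (s) | Before/after, 30 per modality | iHD vs CRRT, 30 per group | iHD vs CRRT, 50 per group |
|---|---|---|---|---|
| 0 | 9.76 | 77% | 50% | 72% |
| 0.3 | 8.16 | 90% | 65% | 86% |
| 0.5 | 6.90 | 97% | 79% | 95% |
| 0.7 | 5.34 | >99% | 95% | >99% |

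Thirty per group is what remains of 50 after the planned loss (50 × 0.60). The 50-per-group column applies if nobody is lost.

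**3. Where 80% is reached.**
- Before/after, 30 per modality: rho 0.063 or more.
- iHD vs CRRT, 30 per group: SD of change at most 6.80 s, i.e. rho 0.515 or more.
- iHD vs CRRT, 40 per group: rho 0.347 or more.
- iHD vs CRRT, 50 per group: SD of change at most 8.84 s, i.e. rho 0.180 or more.

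**4. Shared patients.** With k of n patients per group in both groups, the true variance of the difference in mean change is (1 − k × c/n) times what an independent-groups test assumes. Approximate type I error is 2 × (1 − Φ(1.960/√factor)). Illustration with k = 10, n = 30:
- c = 0.5: factor 0.833, type I error 3.2%.
- c = 0.3: factor 0.900, type I error 3.9%.
- c = −0.3: factor 1.100, type I error 6.2%.

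With 10 of 50 shared the same correlations give 3.9%, 4.3% and 5.7%.

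**The case against.** The strongest reply is that the SAP never claims 80% for iHD vs CRRT. Its wording runs from a CT before dialysis to a difference after dialysis, which reads naturally as a before/after calculation. On that reading 60 is close to a worst case: 77% at rho = 0 and 80% from rho 0.063. This stands, and it is why the point is an unlabelled contrast and not an arithmetic error. It does not remove the problem, because the title and the stated comparison of changes make iHD vs CRRT a central question, and no power is established for it.

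It is also true that the plan is not silent on analysis and attrition: it names the between-group tests and a 40% loss. What is missing is rho or the SD of change.

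A reader might infer that the study is underpowered. The documents do not support that. Rho is unknown, the t-test reaches 80% from rho of about 0.51 at 30 per group, and lower attrition relaxes this to 0.18 at 50. A baseline-adjusted comparison would have about 79%, 82%, 89% and 97% at 30 per group for the four rho values (equal mean baselines, independent groups). The plan does not name that analysis, however, and it is not an obvious main model here: modality is not randomised, and the first CRRT sample is taken within 24 hours of starting CRRT, so it may already reflect treatment.

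A reader might also infer that patients did overlap and that false positives are inflated. The plan permits overlap but gives no count, and with positive correlation the named test is conservative.

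Finally, enrolment ran to January 2023 and the document is dated December 2023, so no power calculation can change recruitment. That limits the power part to how the result is described.

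**Conclusion.** The point holds as a gap in specification. The stated 80% is not tied to a contrast. It is roughly right for the within-modality change (77% or more at any non-negative rho). It is not established for the iHD vs CRRT difference in change, where power at 30 per group runs from about 50% to 95% over rho 0 to 0.7. This is not a finding that the study lacks power.

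The independence problem is conditional on overlap and modest in the illustration: type I error about 3% to 6% against a nominal 5%. The absence of a paired method for the before/after comparisons is plain from the text.

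The power figures apply one SD of 6.9 s and one rho to both groups, although the interval between samples is a 2 to 4 hour session in one and 48 hours in the other. They take the reproducibility-study SD as the between-patient SD in ICU patients, and they cover t-tests, not Mann-Whitney. They show how far the 80% depends on unstated inputs; they do not estimate actual power. Worth correcting, but not fatal.

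**What to change.** 1. Compare the change in CT between modalities by a method that allows for patients in both groups, for example regression of change on modality with cluster-robust standard errors by patient. Report the number of shared patients and a 95% CI for the difference.
2. Use paired t or Wilcoxon signed-rank tests for the before/after comparisons, checking normality on the differences.
3. State which contrast the 60 was calculated for. Qualify the 80%: for iHD vs CRRT at 30 per group it holds only if the SD of change is about 6.8 s or less. Report the observed SD of change.
4. Give a baseline-adjusted model as a sensitivity analysis only, noting the non-randomised modality and the timing of the first CRRT sample.

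Label all of these as post hoc. The cost is SAP wording and a small reanalysis of data already collected, with no added patients or procedures. The power statement may become less favourable, and adjusted and unadjusted results may differ.

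### The between-group t-test assumes equal variances without a safeguard; if group sizes and spreads both differ, the 5% level is not guaranteed, and Welch's test removes the problem at almost no cost

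*Combined protocol and SAP*

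**What the plan says.** The SAP section sets one rule for all continuous outcomes: "Comparisons between groups were performed by using the Student t-test or the Mann-Whitney U test", the first if the data look normal and the second if not. The choice between the two tests rests on normality alone: "The normality of continuous data was assessed through the Shapiro-Wilk test". The section contains no check of equal variances and no unequal-variance version of the t-test. The threshold is fixed: "A P value less than 0.05 was considered statistically significant".

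Under Study outcomes, the change in each outcome, including the primary one (change in EXTEM CT), is compared between iHD and CRRT.

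The two changes cover different intervals. For iHD, "hemodialysis was applied for 2 to 4 hours" (Renal replacement therapy), with samples drawn just before and just after. For CRRT, the second sample follows the first by 48 hours (Laboratory investigations).

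Modality followed clinical need rather than assignment, and a patient treated with both contributes to both groups (Renal replacement therapy). The target is 50 per group after allowing for 40% loss (SAP).

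**The concern.** Student's test is exact for normal data only if both groups share one variance. Nothing in the plan supports that here. One change is measured over an interval 12 to 24 times longer than the other (48/4 to 48/2), in ICU patients whose coagulation status can move in that time. The only SD given describes the level before dialysis ("CT of EXTEM was set as 55 ± 6.9 seconds before dialysis"). No SD of the change is given for either group.

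Equal group sizes would make this harmless, but the plan has no mechanism that keeps the analysed groups equal. The exclusion for CRRT of under 48 hours can apply only to CRRT. The exclusions for blood products and for changes in antithrombotic drugs also have longer to act in CRRT, if the study period means the time between samples.

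If the smaller group has the larger spread, the test declares differences too often. If the larger group has it, the test is conservative and loses power. The normality branch does not help, because skewness is a different matter from unequal spread.

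**Working it through.** **1. What the sample size assumes.** Inputs from the SAP section: difference 5 s, SD 6.9 s, two-sided 5%, power 80%.

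n per group = 2 × (1.96 + 0.8416)² × 6.9² / 5² = 2 × 7.849 × 47.61 / 25 = 29.9, so 30 per group and 60 in total. Then 60 / (1 − 0.40) = 100, or 50 per group. Both stated figures are reproduced, and they rest on a common SD and equal groups.

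**2. What Student's test does when that fails.** Let iHD have n₁ patients and SD 1, and CRRT n₂ patients and SD r. The documents give neither r nor the final group sizes, so both are assumptions.

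- True variance of the mean difference: V = 1/n₁ + r²/n₂
- Variance that Student's test expects: P = [((n₁−1) + (n₂−1)r²)/(n₁+n₂−2)] × (1/n₁ + 1/n₂)
- Approximate error rate: 2Φ(−1.96 × √(P/V))

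Example, 40 iHD/20 CRRT, r = 2:
- V = 1/40 + 4/20 = 0.225
- P = [(39 + 19×4)/58] × 0.075 = 1.983 × 0.075 = 0.1487
- √(P/V) = 0.813, and 2Φ(−1.593) = 11.1%

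Example, 20 iHD/40 CRRT, r = 2:
- V = 1/20 + 4/40 = 0.150
- P = [(19 + 39×4)/58] × 0.075 = 0.2263
- √(P/V) = 1.228, and 2Φ(−2.407) = 1.6%

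At n₁ = n₂, P equals V for any r. The pooled and unequal-variance standard errors then coincide, and only the degrees of freedom differ.

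**3. Simulation.** Normal data with equal means were simulated with 100,000 or more datasets per scenario, so Monte Carlo error is about 0.1 point. All rows have 60 evaluable patients; the loss column is measured from 50 per group.

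| iHD/CRRT | Implied loss iHD, CRRT | Student, r = 1.5 | Student, r = 2 |
|---|---|---|---|
| 30/30 | 40%, 40% | 5.0% | 5.2% |
| 33/27 | 34%, 46% | 6.0% | 6.6% |
| 35/25 | 30%, 50% | 6.8% | 7.8% |
| 40/20 | 20%, 60% | 8.4% | 11.2% |
| 25/35 | 50%, 30% | 3.7% | 3.2% |
| 20/40 | 60%, 20% | 2.7% | 1.7% |

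Welch's test stays at 4.9–5.1% in every scenario tried. With equal SDs, Student's test is at about 5% for any split.

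**4. The Mann-Whitney branch.** At r = 2 it gives 8.5% at 40/20, 5.9% at 30/30 and 3.0% at 20/40. It is no safeguard, but it is not always inflated.

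**5. Power for a 5 s difference.**
- Both SDs 6.9: Student and Welch both 78.8% at 30/30; 87.3% and 87.0% at 50/30; 73.9% and 73.1% at 40/20.
- SDs 6.9 (iHD) and 13.8 (CRRT), 30/50: Student 43.8%, Welch 56.5%. This is the conservative direction, where Student's test gives power away.

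**The case against.** The plan targets equal groups, and with equal groups Student's test is adequate even at a threefold SD ratio (5.1–5.3%). A reader might infer from the 40% loss and the CRRT-only exclusion that the groups will end up unequal. The documents do not establish that. At least 48 hours of CRRT is also an inclusion condition, so patients who fell short may never have counted towards the 50. The plan does not say whether excluded patients were replaced, or whether the 40% covers the exclusions. Unequal spread is likewise inferred from the different intervals. An SD ratio of 2 is a fourfold variance ratio with no source in the documents, and a 40/20 split needs 60% loss in one group against 20% in the other. Milder inputs give milder departures, such as 6.0% at 33/27 with a ratio of 1.5. All of this stands, and it makes the point conditional.

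It is also fair to say that the plan does not state whether the within-modality or the between-group comparison is primary. The 5 s target is worded as "An absolute difference of 5 seconds in CT after dialysis was deemed significant". Reading it as a between-group difference rests on the two-group arithmetic that reproduces 60.

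Finally, Welch's test is not a full repair, because it too assumes independent groups. Take 30/30, equal SDs, 10 to 20 patients in both groups and an assumed within-patient correlation of 0.3 to 0.5. Welch's error rate then falls to between 4.0% and 1.7%.

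None of this defends pooling. The 5% level still depends on conditions that the plan neither states nor checks.

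**Conclusion.** The concern holds as a conditional one. The between-group test has no protection against unequal variances, in a design where unequal spread and unequal sizes are both plausible. If both occur, the 5% level is not kept: over the splits and SD ratios in the table, the error rate runs from 1.7% to 11.2%. The direction depends on which group has the larger spread. If either condition is absent, the level stays near 5%.

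A reader might go further and conclude that the reported P values are too small, or that the error rate has been breached. The documents do not support that: they give no SD of the change and no final group sizes, and the departure could go either way. The figures above also assume normal data and independent groups. This is a low-cost improvement in method, not a demonstrated error in the results.

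**What to change.** Replace Student's test with Welch's unequal-variance t-test for the between-group comparison of the change in EXTEM CT and of the other continuous outcomes. Report the mean difference with its 95% CI, the SD of the change and the number analysed in each group, so that readers can see whether the choice mattered.

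Enrolment ran to January 2023 and the document is dated December 20, 2023, so this should be described as a re-analysis of existing data, not as pre-specified. If Welch's and Student's results agree, say so, and the matter is settled for this study.

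State how many patients contribute to both groups and deal with them separately, for example by a model that allows for within-patient correlation or by a sensitivity analysis that counts each patient once.

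The cost is a sentence in the SAP and a short re-run. Where the SDs are in fact equal, the loss of power is under one percentage point.

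### The between-modality comparison of change uses the pooled-variance Student t-test, although the design gives reason to doubt equal variances and equal analysed group sizes; Welch's test avoids the risk at almost no cost.

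*Combined protocol and SAP*

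**What the plan says.** The section on study outcomes defines the primary endpoint as a change: "The primary study outcome was changes in CT of EXTEM after dialysis". It then sets up the comparison between modalities: "To identify differences in changes according to dialysis modality, a comparison of each study outcome was made between the iHD group and the CRRT group".

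The SAP gives the test for normally distributed variables: "Comparisons between groups were performed by using the Student t-test". For the others it names the Mann-Whitney U test. The choice between the two rests on normality alone: "The normality of continuous data was assessed through the Shapiro-Wilk test". No check of variances and no unequal-variance t-test is mentioned.

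The two changes are measured over different windows. For iHD, samples are drawn just before and just after the session, and "hemodialysis was applied for 2 to 4 hours depending on the clinical condition of patients". For CRRT, "the second samples were taken 48 hours after collection of the first samples".

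Modality follows clinical need; it is not randomised. The section on design and patients excludes CRRT lasting under 48 hours. It also excludes patients for blood products, for starting or stopping antithrombotic drugs, and for laboratory errors; these are worded for all patients.

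The SAP sizes the study at 60 patients and, with a single 40% loss allowance, raises this to 50 per group.

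**The concern.** The pooled-variance t-test estimates one common variance, weighted towards the larger group. If the smaller group has the larger spread, the pooled standard error is too small and the test rejects too often. If the larger group has the larger spread, the standard error is too large and power is lost.

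Both ingredients are plausible here. The CRRT window is 12 to 24 times as long as the iHD window (48/4 to 48/2), in critically ill patients, so nothing suggests that the two changes vary equally. Nothing in a non-randomised design secures equal analysed numbers either. One exclusion can touch only CRRT. If the transfusion and drug-change exclusions are counted between the two samples, they too have far longer to operate in CRRT.

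At stake is the error rate of the between-modality test of the primary outcome and of every secondary change that goes through the t-test branch.

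**Working it through.** **1. The plan's own figure.** Inputs from the SAP: difference 5 s, SD 6.9 s (CT before dialysis), two-sided 0.05, power 80%. With the normal approximation for two independent means:

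n per group = 2 × (1.960 + 0.842)² × 6.9² / 5² = 29.9, so 30 per group and 60 in total. Then 30 / (1 − 0.40) = 50 per group, 100 in total. Both stated figures are reproduced. The calculation implies about 30 v 30 analysed if losses are equal.

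**2. Inputs the documents do not give.** There is no SD of the change for either modality and no loss by group. The CRRT:iHD SD ratio (1 to 3) and the group splits below are therefore assumptions.

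**3. How far off the pooled standard error is.** Set the iHD SD to 1 and the CRRT SD to r.

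- Pooled variance: s² = [(n₁ − 1) + (n₂ − 1)r²] / (n₁ + n₂ − 2)
- Squared standard error used by Student's test: s²(1/n₁ + 1/n₂)
- True squared standard error: 1/n₁ + r²/n₂

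For iHD 40, CRRT 20 and r = 2: s² = (39 + 19 × 4)/58 = 1.983. The squared standard error used is 1.983 × 0.075 = 0.149. The true value is 1/40 + 4/20 = 0.225. The standard error used is √(0.149/0.225) = 0.81 of the true one.

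For 30 v 30 and r = 2: s² = 2.5, the value used is 2.5 × 0.0667 = 0.167, and the true value is 1/30 + 4/30 = 0.167. The ratio is exactly 1, which is why equal sizes protect the test.

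**4. Rejection rates when mean changes are equal.** Simulation of independent normal samples, 200,000 studies per setting, two-sided 0.05. Losses are counted from 50 per group.

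| iHD v CRRT | Losses iHD / CRRT | SE used ÷ true SE, r = 2 | Student, r = 1.5 | r = 2 | r = 3 |
|---|---|---|---|---|---|
| 30 v 30 | 40% / 40% | 1.00 | 5.0% | 5.1% | 5.3% |
| 35 v 25 | 30% / 50% | 0.90 | 6.7% | 7.8% | 9.0% |
| 50 v 30 | 0% / 40% | 0.86 | 7.7% | 9.4% | 11.2% |
| 40 v 20 | 20% / 60% | 0.81 | 8.6% | 11.2% | 14.0% |
| 45 v 15 | 10% / 70% | 0.73 | 10.8% | 15.3% | 20.6% |
| 20 v 40 | 60% / 20% | 1.23 | 2.6% | 1.7% | 1.1% |

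Welch's test rejects in 4.9-5.2% of studies in every one of these settings.

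**5. Price of Welch's test if variances are in fact equal.** Simulated power for a 5 s difference with SD 6.9 s in both groups, Student v Welch: 78.7% v 78.7% at 30 v 30, 77.7% v 77.5% at 35 v 25, 74.1% v 73.3% at 40 v 20, and 66.7% v 64.5% at 45 v 15. The 30 v 30 figure is a little under 80% because step 1 uses the normal approximation.

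**The case against.** The strongest reply is that the plan, taken at its word, is not harmed. It applies one allowance to both groups ("Considering a loss to follow-up of 40" per cent) and aims for 50 in each, so about 30 v 30 analysed, where Student's test keeps its 5% at every SD ratio examined. This stands. Inflation needs two unproven conditions together: a more variable CRRT change and a clearly smaller CRRT group.

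A reader might infer that losses do fall more on CRRT and that the true error is therefore 11-15%. The documents do not support that. They give no loss by group, and those rates need an SD ratio of 2 together with CRRT losses of 60-70% against 10-20% in iHD. At least 48 hours of CRRT (or an iHD session) is also a condition of entry, and the plan does not say whether patients falling short count against the 50 places. So that exclusion may not shrink the analysed group at all.

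A reader might also take equal spread to be part of the hypothesis under test. It is an assumption of the test; with equal sizes, unequal spread alone causes almost no false rejections.

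The normality gate gives some relief, but only under one reading. If Shapiro-Wilk is run on both groups pooled (the SAP does not say), unequal spread sends some studies to the Mann-Whitney branch. At 40 v 20 the Student rejection rate among those remaining is then 9.0% at ratio 2 and 11.1% at ratio 3. Testing each group separately gives no such relief. Nor is the Mann-Whitney branch immune: at ratio 2 it rejects in 5.8% of studies at 30 v 30, 8.5% at 40 v 20 and 10.4% at 45 v 15.

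Finally, patients treated with both modalities contribute data to both groups. Welch's test also assumes independent groups, so its 5% is shown only for that case.

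**Conclusion.** The point holds in conditional form. The SAP relies on an equal-variance assumption that its own sampling windows make doubtful, and nothing in the design guarantees the equal group sizes that would make the assumption harmless. Under the planned equal sizes the type-I error is about 5%. Over the assumed splits and SD ratios in the table it runs from about 1% to about 21%. A milder case, such as 35 v 25 at ratio 2, gives about 8%. The documents do not show where in that range the study falls. This is a recommended improvement to the analysis, not a demonstrated error in the result.

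**What to change.** In the SAP, replace the Student t-test with Welch's unequal-variance t-test for all between-modality comparisons of change, with no preliminary test of variances. Report the mean difference with its Welch 95% confidence interval, and give the number analysed and the SD of change for each modality, so that a reader can see whether the issue arose.

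The cost is a short change to the SAP text. If variances are equal, the loss of power is under 1 percentage point at 30 v 30, 35 v 25 and 40 v 20, and about 2 points at 45 v 15 (step 5). The change does not deal with patients who appear in both groups; that is a separate issue and needs its own provision.
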